3.5.2.2. Systemic Events

Systemic events reported via the e-diary are fever, fatigue, headache, vomiting, nausea, diarrhea, muscle pain, and joint pain. The participant is to document the presence or absence of systemic events in the e-diary as “Mild,” “Moderate,” “Severe,” or “None.” Participants are to be asked to assess the severity of each event according to [Table 5](#) below.

Only an investigator is able to classify a maternal participant’s systemic event as Grade 4, after physical evaluation of the maternal participant or documentation from another medically qualified source (eg, emergency room or hospital record) or contact with the participant. If a maternal participant experiences a Grade 4 systemic event, the investigator must immediately notify the sponsor. A Grade 4 event will be collected on the unscheduled reactogenicity page and as an AE on the CRF. The event will be graded using the AE

severity grading scale (see Section 10.3.3 of the protocol). Further, for all ongoing systemic events on Day 7, the stop date will be recorded in the CRF.

Table 5. Grading Scale for Systemic Events

	Mild Grade 1	Moderate Grade 2	Severe Grade 3	Grade 4^a
Fatigue (= tiredness in diaries)	Does not interfere with activity	Some interference with activity	Prevents daily routine activity	Emergency room visit or hospitalization for severe fatigue
Headache	Does not interfere with activity	Some interference with activity	Prevents daily routine activity	Emergency room visit or hospitalization for severe headache
Vomiting	1 to 2 times in 24 hours	>2 times in 24 hours	Requires intravenous hydration	Emergency room visit or hospitalization for severe vomiting
Nausea	Does not interfere with activity	Some interference with activity	Prevents daily routine activity	Emergency room visit or hospitalization for severe nausea
Diarrhea	2 to 3 loose stools in 24 hours	4 to 5 loose stools in 24 hours	6 or more loose stools in 24 hours	Emergency room visit or hospitalization for severe diarrhea
Muscle pain	Does not interfere with activity	Some interference with activity	Prevents daily routine activity	Emergency room visit or hospitalization for severe muscle pain
Joint pain	Does not interfere with activity	Some interference with activity	Prevents daily routine activity	Emergency room visit or hospitalization for severe joint pain

- a. Only an investigator is able to classify a maternal participant's systemic event as Grade 4, after clinical evaluation of the maternal participant or documentation from another medically qualified source (eg, emergency room or hospital record) or contact with the maternal participant. Grade 4 assessment should be made by the investigator using the AE severity grading scale. The assessment will be collected on the AE case report form.

The highest temperature for each day for 7 days after vaccination is to be recorded in the e-diary. The protocol defines fever as an oral temperature $\geq 100.4^{\circ}\text{F}$ ($\geq 38.0^{\circ}\text{C}$). For ongoing fever on Day 7, the stop date will be recorded in the CRF. Any temperatures recorded as $< 35.0^{\circ}\text{C}$ or $> 42.0^{\circ}\text{C}$ will be treated as data-entry errors and excluded from the analyses. For reporting purposes, fever will be analyzed using the following temperature grading scale as displayed in [Table 6](#).

Table 6. Grading Scale for Fever

Mild Grade 1	Moderate Grade 2	Severe Grade 3	Grade 4
≥38.0°C to 38.4°C	>38.4°C to 38.9°C	>38.9°C to 40.0°C	>40.0°C

The presence or absence of each systemic event on a given day is defined as follows:

- = “Missing,” if the value is missing on a given day;
- = “Yes,” if the participant reports a temperature ≥38.0°C for fever **or** “Mild,” “Moderate,” “Severe,” or “Grade 4” for the remaining events on a given day;
- = “No,” if the participant reports a temperature <38.0°C for fever **or** “None” for the remaining events on a given day.

For each systemic event, the following variables will be derived:

1. Presence or absence of each systemic event on each day (Days 1-7) after vaccination.
2. Presence or absence of each systemic event on “any day (Day 1-7)” after vaccination.
3. Maximum severity of each systemic event on “any day (Day 1-7)” after vaccination.
4. Presence or absence of any systemic event on “any day (Day 1-7)” after vaccination.
5. Duration of each systemic event after vaccination.
6. Onset day of each systemic event after vaccination.
7. Onset day of any systemic event after vaccination.

The derivation of these variables is similar to the derivation of the variables for local reactions ([Section 3.5.2.1](#)). “Any systemic event” includes any fever, fatigue, headache, vomiting, nausea, diarrhea, muscle pain, or joint pain.

CCI

CCI

3.5.4. Laboratory Data

Blood samples for hematology and blood chemistry assessments (approximately 10 mL) will be collected for all maternal participants at screening.

Assessments will include:

- Hematology: hemoglobin, hematocrit, red blood cell (RBC) count, platelet count, white blood cell (WBC) count, total neutrophils (absolute [Abs]), eosinophils (Abs), monocytes (Abs), basophils (Abs), and lymphocytes (Abs).
- Blood chemistries: alanine aminotransferase (ALT), aspartate aminotransferase (AST), alkaline phosphatase, total bilirubin, blood urea nitrogen (BUN), and creatinine.

The toxicity grading scale in [Table 7](#) below for pregnant women will be adapted, as appropriate (eg, based on the pregnancy status at the visit), for grading laboratory test abnormalities.

Table 7. Hematology and Blood Chemistry Toxicity Grading Scale

	Pregnancy Status	Normal Range	Mild (Grade 1)	Moderate (Grade 2)	Severe (Grade 3)	Grade 4
Female hemoglobin (Hb), g/dL	Second trimester	9.7-14.8	9.0-9.6	8.0-8.9	7.0-7.9 or requires a transfusion	<7.0 or life-threatening acute blood loss
	Change from baseline		1.6-2.0	2.1-4.5	4.6-5.0	>5.0
	Third trimester	9.5-15.0	9.0-9.4	8.0-8.9	7.0-7.9 or requires a transfusion	<7.0 or life-threatening acute blood loss
	Change from baseline		1.6-2.0	2.1-4.5	4.6-5.0	>5.0
Platelets high, 1000 cells/mm³	Second trimester	155-409	410-499	500-749	750-1000	>1000
	Third trimester	146-429	430-499	500-749	750-1000	>1000
Platelets low, 1000 cells/mm³	Second trimester	155-409	125-154	100-124	25-99	<25
	Third trimester	146-429	125-146	100-124	25-99	<25
WBCs^a high, 1000 cells/mm³	Second trimester	5.6-14.8	>14.8-16.0	>16.0-20.0	>20.0-25.0	>25.0 signs of septic shock
	Third trimester	5.9-16.9	>16.9-18.0	>18.0-20.0	>20.0-25.0	>25.0 signs of septic shock
WBCs^a low, 1000 cell/mm³	Second trimester	5.6-14.8	<5.5-3.5	<3.5-1.4	<1.4-1.0	<1.0 signs of septic shock
	Third trimester	5.9-16.9	<5.9-3.5	<3.5-1.4	<1.4-1.0	<1.0 signs of septic shock
Neutrophils (absolute neutrophil count), 1000 cells/mm³	Second trimester	3.8-12.3	<3.8-2.0	<2.0-1.0	<1.0-0.5	<0.5
	Third trimester	3.9-13.1	<3.9-2.0	<2.0-1.0	<1.0-0.5	<0.5
Eosinophils (absolute), 1000 cells/mm³	Second trimester	0-0.6	>0.6-1.5	>1.5-5.0	>5.0	Hypereosinophilic
	Third trimester	0-0.6	>0.6-1.5	>1.5-5.0	>5.0	Hypereosinophilic
Monocytes (absolute), 1000 cells/mm³	Second trimester	0.1-1.1	≤10% outside normal range	>10% outside range: clinical correlation may be necessary and grading according to it		
	Third trimester	0.1-1.4	≤10% outside normal range	>10% outside range: clinical correlation may be necessary and grading according to it		
Basophils (absolute), 1000 cells/mm³	Second trimester	0-0.1	≤10% outside normal range	>10% outside range: clinical correlation may be necessary and grading according to it		
	Third trimester	0-0.1	≤10% outside normal range	>10% outside range: clinical correlation may be necessary and grading according to it		
Lymphocytes high (absolute), 1000 cells/mm³	Second trimester	0.9-3.9	>3.9-5.0	>5.0		
	Third trimester	1.0-3.6	>3.6-5.0	>5.0		

Table 7. Hematology and Blood Chemistry Toxicity Grading Scale

	Pregnancy Status	Normal Range	Mild (Grade 1)	Moderate (Grade 2)	Severe (Grade 3)	Grade 4
Lymphocytes low (absolute) 1000 cells/mm ³	Second trimester	0.9-3.9	<0.9-0.75	<0.75-0.5	<0.5-0.25	<0.25
	Third trimester	1.0-3.6	<1.0-0.75	<0.75-0.5	<0.5-0.25	<0.25
Blood urea nitrogen (BUN), mg/dL	Second trimester	3-13	14-19	20-30	>30	Requires dialysis
	Third trimester	3-11	12-19	20-30	>30	Requires dialysis
Creatinine, mg/dL	Second trimester	0.4-0.8	0.9-1.2	1.3-1.6	1.7-2.5	>2.5 or requires dialysis
	Third trimester	0.4-0.9	1-1.2	1.3-1.6	1.7-2.5	>2.5 or requires dialysis
Aspartate aminotransferase (AST^b), U/L	Second trimester	3-33	>1.0-1.2 x ULN ^c	>1.2-3.0 x ULN ^c	>3.0-8.0 x ULN ^c	>8.0 x ULN ^c cirrhosis transplant candidate
	Third trimester	4-32	>1.0-1.2 x ULN ^c	>1.2-3.0 x ULN ^c	>3.0-8.0 x ULN ^c	>8.0 x ULN ^c cirrhosis transplant candidate
Alanine aminotransferase (ALT^d), U/L	Second trimester	2-33	>1.0-1.2 x ULN ^c	>1.2-3.0 x ULN ^c	>3.0-8.0 x ULN ^c	>10 x ULN ^c
	Third trimester	2-25	>1.0-1.2 x ULN ^c	>1.2-3.0 x ULN ^c	>3.0-8.0 x ULN ^c	>8.0 x ULN ^c cirrhosis transplant candidate
Total bilirubin (with increased LFTs^e), mg/dL	Second trimester	0.1-0.8	>1.0-1.2 x ULN ^c	>1.2-1.5 x ULN ^c	>1.5-1.8 x ULN ^c	>1.8 x ULN ^c
	Third trimester	0.1-1.1	>1.0-1.2 x ULN ^c	>1.2-1.5 x ULN ^c	>1.5-1.8 x ULN ^c	>1.8 x ULN ^c
Total bilirubin (with normal LFTs^e), mg/dL	Second trimester	0.1-0.8	>1.0-1.5 x ULN ^c	>1.5-2.0 x ULN ^c	>2.0-3.0 x ULN ^c	>3.0 x ULN ^c
	Third trimester	0.1-1.1	>1.0-1.5 x ULN ^c	>1.6-2.0 x ULN ^c	>2.0-3.0 x ULN ^c	>3.0 x ULN ^c
Alkaline phosphatase, U/L	Second trimester	25-126	1.1-2.0 x ULN ^c	>1.2-3.0 x ULN ^c	>3.0-8.0 x ULN ^c	>8.0 x ULN ^c
	Third trimester	38-229	>1.0-1.2 x ULN ^c	>1.2-3.0 x ULN ^c	>3.0-8.0 x ULN ^c	>8.0 x ULN ^c

- a. WBC = white blood cell.
- b. AST = aspartate aminotransferase.
- c. ULN = upper limit of normal.
- d. ALT = alanine aminotransferase.
- e. LFT = liver function test.

3.5.5. Physical Examination, Including Vital Signs

3.5.5.1. Physical Examination, Including Vital Signs: Maternal Participants

Physical examination will be performed at the screening visit (Visit 0) and will include any clinically significant abnormalities within the following body systems: general appearance; skin; head, eyes, ears, nose, and throat; heart; lungs; abdomen; musculoskeletal; extremities; neurological; and lymph nodes. Height and weight will also be measured and recorded.

Vital signs including sitting systolic and diastolic blood pressure, heart rate, and oral temperature will be measured at the screening visit (Visit 0), prior to vaccination on Day 1, at the 2-week follow-up, and at the 1-month follow-up and recorded in the CRF.

3.5.5.2. Physical Examination, Including Vital Signs: Infant Participants

The physical examination will be performed at all scheduled visits and will include any clinically significant abnormalities within the following body systems: general appearance; skin; head, eyes, ears, nose, and throat; heart; lungs; abdomen; back; musculoskeletal; extremities; genitourinary; neurological; and lymph nodes.

Length, head circumference, and weight will also be measured and recorded.

Rectal temperature, heart rate, and respiratory rate will be assessed at all visits; additionally, oxygen saturation by pulse oximetry will be assessed at birth ^{CCI} [REDACTED]. All attempts should be made to help ensure that measurements are taken while the infant is resting quietly.

3.5.6. Obstetric Examination

Obstetric examination findings will be collected at screening through the 1-month follow-up visit. The obstetric examination will include, but is not limited to, scars from previous deliveries, fundal height, fetal heart tones, and fetal movement.

The following information regarding pregnancy outcome will be collected: date of delivery, location of delivery (medical facility, home, other), mode of delivery (vaginal, cesarean section), cesarean type (elective, semielective, emergency), delivery complications (yes, no), number of births, outcome at delivery (full-term live birth, premature live birth, stillbirth, spontaneous abortion, induced/elective abortion), gross visual inspection of the aborted fetus/stillbirth (not done, no observed abnormalities, observed abnormalities), and pathology performed (yes, no).

3.5.7. Birth Outcome: Infant Participants

Infant outcome at birth will be collected at the delivery visit and includes the following: gestational age (weeks, days); Apgar (appearance, pulse, grimace, activity, and respiration) score at 1, 5, and 10 minutes; Ballard score; infant cry immediately after delivery (yes, no); infant suckle shortly after delivery (yes, no); newborn normal (yes, no); congenital malformation/anomaly (yes, no); and other neonatal problem/abnormality (yes, no). Infant vital status (live, stillbirth) will also be included. Neonatal death will be derived using the

response to “delivery outcome” from the pregnancy outcome and the AE data. Neonatal death is defined as the death of a live-born infant that occurred within a month after birth.

4. ANALYSIS SETS (POPULATIONS FOR ANALYSIS)

Data for all participants will be assessed to determine if participants meet the criteria for inclusion in each analysis population prior to unblinding and releasing the database and classifications will be documented per standard operating procedures.

Population	Description
Enrolled	All participants who sign the informed consent document.
Randomly assigned to investigational product	All maternal participants who are assigned a randomization number in the interactive response technology (IRT) system.
Evaluable – Maternal	All maternal participants who: 
 • are eligible; • receive the investigational product to which they were randomized; • have blood drawn for assay testing within the protocol-specified time frames ; • have at least 1 valid and determinate assay result after vaccination; and • have no major protocol violations. Participants will be analyzed according to the investigational product as randomized.
Evaluable – Infant	All infant participants who: 
 • are eligible; • are born to the maternal participants who received the investigational product to which they were randomized and who have no major protocol violations before delivery; • have blood drawn for assay testing within the protocol-specified time frame at birth^a; • have at least 1 valid and determinate assay result at birth^a; and • have no major protocol violations. Participants will be analyzed according to the investigational product as randomized to their mothers.
Modified intent-to-treat (mITT) – Maternal	All randomized maternal participants who receive investigational product and have at least 1 valid and determinate assay result for the proposed analysis. Participants will be analyzed according to the investigational product as randomized.
mITT – Infant	All infant participants who are born to vaccinated maternal participants and have at least 1 valid and determinate assay result for the proposed analysis. Participants will be analyzed according to the investigational product as randomized to their mothers.
Safety – Maternal	All randomized maternal participants who receive investigational product. Participants will be analyzed according to the investigational product they actually received. A randomized participant who did not receive investigational product will be excluded from the safety analyses.

Population	Description
Safety – Infant	All infant participants who are born to vaccinated maternal participants. Participants will be analyzed according to the investigational product their mothers actually received. An infant born from a randomized maternal participant who did not receive investigational product will be excluded from the safety analyses.

- a. Cord blood sample must be obtained on the day of birth. If cord blood is unavailable, a venous blood sample is to be collected up to 24 hours after birth.

Major protocol violations will be determined by clinical review (through the data handling memo). A major protocol violation is a protocol violation that, in the opinion of the sponsor’s study medical monitor, would materially affect assessment of immunogenicity, eg, participant receipt of a prohibited vaccine or medication that might affect immune response or a medication error with suspected decrease in potency of the vaccine. The sponsor’s medical monitor will identify those participants with protocol violations before any immunogenicity analysis is carried out.

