6.5. Concomitant Therapy

6.5.1. Prohibited Concomitant Treatments – Maternal Participants

- Investigational vaccines, drugs, or medical devices are prohibited during the course of the study.
- Blood/plasma products or immunoglobulins (except Rho(D) immune globulin [eg, RhoGam], which can be given at any time) and immunosuppressive therapy are prohibited during the course of the study.
- Nonstudy vaccines may not be given concomitantly with the investigational product or within 6 days after investigational product administration (Day 1 to Day 7), except if medically necessary (eg, during an outbreak or pandemic situation).

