9.1.1. Estimands – Maternal Participants

9.1.1.1. Safety:

In maternal participants receiving 1 dose of investigational product:

- The percentage of maternal participants reporting local reactions
- The percentage of maternal participants reporting systemic events
- The percentage of maternal participants reporting AEs

- The percentage of maternal participants reporting obstetric complications, MAEs, and SAEs

Missing e-diary data will not be imputed; missing AE dates and missing AE intensity will be handled according to Pfizer safety rules.

9.1.1.2. Immunogenicity:

In maternal participants receiving 1 dose of investigational product and in compliance with the key protocol criteria (evaluable participants):

- The immune response, estimated by the GMT for RSV A– and RSV B–neutralizing antibody titers
- The immune response, estimated by the GMFR from baseline in RSV A– and RSV B–neutralizing antibody titers
- GMR, estimated by the ratio of the GMTs for RSV A– and RSV B–neutralizing antibody titers of the RSV vaccine group and the placebo group

These estimands estimate the vaccine effect in the hypothetical setting where participants follow the study schedules and protocol requirements as directed. Missing serology results will not be imputed, as missing completely at random (MCAR) is assumed. For participants who discontinue from the study or have major protocol violations, all postdiscontinuation or violation observations will be censored.

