2.1.5. Secondary Estimands

2.1.5.1. Secondary Estimands: Maternal Participants

- **Immune response estimated by the geometric mean titer (GMT) for RSV A– and RSV B–neutralizing antibody titers.**

This estimand estimates the vaccine effect in the hypothetical setting where participants follow the study schedules and protocol requirements as directed. It includes the following 4 attributes:

- Population: Maternal participants receiving 1 dose of investigational product and in compliance with key protocol criteria (evaluable participants).
- Variable: Antibody titer results before vaccination, 2 weeks and 1 month after vaccination, and at delivery.
- Intercurrent event(s): For participants who discontinue or have major protocol violations, all postdiscontinuation or postviolation observations will be censored. Results obtained from out-of-window blood draws will also be removed. Missing serology results will not be imputed, as missing completely at random (MCAR) is assumed.
- Population-level summary: GMT for RSV A– and RSV B–neutralizing antibody titers.

- **Immune response estimated by the geometric mean fold rise (GMFR) from baseline in RSV A– and RSV B–neutralizing antibody titers.**

This estimand estimates the vaccine effect in the hypothetical setting where participants follow the study schedules and protocol requirements as directed. It includes the following 4 attributes:

- Population: Maternal participants receiving 1 dose of investigational product and in compliance with key protocol criteria (evaluatable participants).
 - Variable: Fold rise from before vaccination to 2 weeks and 1 month after vaccination and at delivery in antibody titers.
 - Intercurrent event(s): For participants who discontinue or have major protocol violations, all postdiscontinuation or postviolation observations will be censored. Results obtained from out-of-window blood draws will also be removed. Missing serology results will not be imputed, as MCAR is assumed.
 - Population-level summary: GMFR from baseline for RSV A– and RSV B–neutralizing antibody titers.
- **Geometric mean ratio (GMR) estimated by the ratio of the GMT for RSV A– and RSV B–neutralizing antibody titers of the RSV vaccine group to the placebo group.**

This estimand estimates the vaccine effect in the hypothetical setting where participants follow the study schedules and protocol requirements as directed. It includes the following 4 attributes:

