6.2.1.1.1. Main Analysis

- Estimand strategy: Hypothetical.
- Analysis set: Evaluable (Section 4). Maternal participants receiving 1 dose of investigational product and in compliance with key protocol criteria.
- Analysis methodology: Descriptive summary statistics.

- Intercurrent events and missing data: All postdiscontinuation or postviolation observations will be censored. Results obtained from out-of-window blood draws will also be removed. Missing results will not be imputed.
- GMTs of the RSV A– and RSV B–neutralizing antibody titers at each available time point will be descriptively summarized for each vaccine group, along with associated 2-sided 95% CIs.
- GMFRs and associated 2-sided 95% CIs will be provided for RSV A– and RSV B–neutralizing antibody titers from before vaccination to each available time point after vaccination for each vaccine group.
- GMRs of the RSV vaccine group to the placebo group for the RSV A– and RSV B–neutralizing antibody titers at each available time point after vaccination will be calculated, along with associated 2-sided 95% CIs.
- RCDCs for RSV A– and RSV B–neutralizing antibody titers for a combination of prespecified time points and vaccine groups will be generated.
- Bar graphs of prevaccination and 1-month-postvaccination neutralizing GMTs will be produced for each vaccine group.

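### The evaluable sets exclude a participant for a major protocol violation at any time, although the estimands censor only later results, so a late violation deletes valid earlier titers

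*SAP*

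**What the plan says.** Two rules deal with major protocol violations, and both apply to the same analyses.

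**Set rule.** SAP section 4 (Evaluable – Maternal) requires that women "have no major protocol violations. Participants will be analyzed according to the investigational product as randomized". Protocol 9.3 has the same untimed condition. In Evaluable – Infant the infant's own violations are likewise untimed. The mother's violations are limited: infants qualify if born to mothers "who have no major protocol violations before delivery".

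**Result rule.** SAP 2.1.5.1 states: "For participants who discontinue or have major protocol violations, all postdiscontinuation or postviolation observations will be censored". SAP 2.1.5.2 repeats this for infants. The main analyses (SAP 6.2.1.1.1 and 6.2.2.1.1) name the evaluable set as their analysis set and carry the same rule: "All postdiscontinuation or postviolation observations will be censored. Results obtained from out-of-window blood draws will also be removed". Protocol 9.1.1 agrees: "For participants who discontinue from the study or have major protocol violations, all postdiscontinuation or violation observations will be censored"; Protocol 9.1.2 has the infant counterpart.

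Under SAP section 4, the sponsor's medical monitor decides what counts as major, judged by material effect on the immunogenicity assessment. That test is not tied to a time point. Under SAP 6.2.1.1.2 and 6.2.2.1.2 the mITT repeat runs only if the two populations differ by about 10%. Under SAP 6.4 the immunogenicity subgroup analyses use the evaluable population alone.

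**The concern.** Censoring what follows a violation presupposes that what came before it is kept. The evaluable set does not keep it, because it removes the whole participant. In the main analysis the set definition is applied first, so no violator remains for the violation part of the censoring rule to act on. The estimand and its analysis set therefore give different answers for the same woman.

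The conflict matters because violations can occur long after the titers of interest. Protocol 6.5.1 says blood and plasma products, immunoglobulins (with one exception) and "immunosuppressive therapy are prohibited during the course of the study", and participation runs to about 12 months after delivery. If an event of this kind at or after delivery is ruled major, the set rule deletes baseline, 2-week and 1-month titers that it could not have affected. An infant's own later violation similarly deletes its birth titer.

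Three things are at stake:

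- Two programmers could build different datasets from this SAP.
- SAP 7.2 plans analyses from 250 births onward, so a 1-month titer reported then could be missing from the final analysis because of something that happened later.
- SAP section 2 says the study will supply the data for choosing dose and formulation.

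**Working it through.** **No figure to reproduce on this point.** The plan gives no violation rate. The only calculated figures in Protocol 9.2 are in Table 6. They reproduce (for example 1 − 0.99^100 = 0.634 against 0.63) but have no bearing here.

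**Side by side.** Take a woman with titers before vaccination, at 2 weeks, at 1 month and at delivery.

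| First major violation | Result rule keeps | Set rule keeps | Valid titers lost |
|---|---|---|---|
| Between 1-month and delivery draws | 3 | 0 | 3 |
| After the delivery draw | 4 | 0 | 4 |

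For an infant with a birth sample and two later draws, a violation between the two later draws leaves 2 titers under the result rule and 0 under the set rule.

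**Size, on stated assumptions**

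- Arm size: up to 650 women (Protocol 4.1.2) split equally over five groups, 650/5 = 130.
- Share v of women whose first major violation falls between the 1-month and delivery draws: 2% to 5%. This is an assumption.
- Data otherwise complete, giving 4 × 130 = 520 maternal titers per arm.

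Women affected: 130 × 0.02 = 2.6, about 3; 130 × 0.05 = 6.5, about 7.

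Titers kept with k women affected:

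- Set rule, 4(130 − k): 508 for k = 3; 492 for k = 7.
- Result rule, 3 × 130 + (130 − k): 517 for k = 3; 513 for k = 7.
- Difference, 3k: 9 and 21 valid titers per arm.

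Confidence-interval width on the log scale at the three earlier time points, ratio 1/√(1 − v): 1/√0.98 = 1.010; 1/√0.95 = 1.026. That is about 1% to 3% wider.

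Possible shift in an earlier GMT if the dropped women's true GMT is f times that of the rest, ratio f^(−v): at v = 5%, f = 0.5 gives 1.035 and f = 2 gives 0.966. Even a twofold difference moves the GMT by about 3.5%.

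**Against the mITT trigger.** Ten per cent of 130 is 13 women. A loss of 3 to 7 from late violations would not, by itself, prompt the mITT repeat.

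**Subgroups.** SAP Table 8 has four gestational-age bands. With an even spread (assumption), 130/4 is about 32 women per arm per band, so one late violator is about 3% of a cell, and SAP 6.4 provides no mITT version.

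**The case against.** The case against has real weight.

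- **Modest effect.** The endpoints are secondary, all analyses are descriptive (SAP 5.1), and the 2-5% is assumed. This stands.
- **Medical-monitor discretion.** The listed maternal secondary titers end at delivery, so the monitor might not rule a later event major. That could soften the problem, but nothing ties the ruling to a time point, and once an event is ruled major the set rule is absolute.
- **Transparency.** SAP 6.5.2 reports exclusions with reasons, SAP section 4 has populations classified before unblinding, and SAP 7.2 openly allows preliminary evaluable populations. This makes the loss visible but does not settle which rule applies. Nor can a violation occurring after the first planned analysis have been identified before it.
- **The censoring sentence is not empty.** It also covers discontinuation, and it can act in an mITT repeat, where violators are present. The claim that it has nobody to act on holds only for violations in the main, evaluable-set analysis.

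A reader might also infer that one out-of-window draw removes all of a woman's titers, because the set requires that women "have blood drawn for assay testing within the protocol-specified time frames". The documents do not support that. The plural is only ambiguous: the same definition asks for just one valid post-vaccination result, the analyses remove out-of-window results rather than participants, and SAP version 2 reworded the set because not every woman has a 1-month visit. Only the 2-week and 1-month post-vaccination draws have stated windows; the delivery window is given as variable in the protocol's schedule of activities. Even read strictly, with independent out-of-window probability q per draw, 130(1 − q)² leaves about 117 women at q = 5% or 105 at q = 10%. Losses of 10-19% would reach the mITT trigger.

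**Conclusion.** The conflict is real, and it is in both documents: an untimed, whole-participant exclusion in SAP section 4 and Protocol 9.3, against result-level censoring in Protocol 9.1, SAP 2.1.5 and the SAP main analyses. Applied as written, the set rule overrides the estimand and discards valid pre-violation titers.

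The size rests on two assumptions, 130 women per arm and 2-5% late violators: about 3-7 women per arm, and intervals about 1-3% wider at the earlier time points. This is a correction the plan should make, not a threat to its main conclusions.

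A reader might go further and infer that the loss is informative because such violations follow obstetric complications, or that it tilts the comparison between doses. The first is plausible but undocumented. For the second, nothing shows a difference between arms.

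**What to change.** Make the evaluable sets specific to the time point, in SAP section 4 and Protocol 9.3. For each analysed time point, include a participant who:

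- is eligible;
- received the randomised product (for infants, whose mother did);
- had that draw within its own window, where one is stated, with a valid and determinate result; and
- had no major protocol violation before that draw.

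Keep the existing before-delivery limit on the mother's violations in the infant set, and apply the draw-date timing to the infant's own violations. State that a fold rise or transfer ratio needs both of its draws to qualify. Say whether the current requirement for a valid birth sample still applies to later infant time points, and whether the 10% mITT comparison is made per time point. This wording also removes the ambiguity about draw windows.

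If whole-participant exclusion is really intended, the alternative is to delete the post-violation censoring text and restate the estimands. The time-point form is preferable because it matches the estimand already written and the timing already used for the mother's violations in the infant set.

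The cost is a wording change and one programming flag per visit. Sample sizes will differ by time point, but they already do, since missing results are not imputed and out-of-window results are removed. Protocol section 9 lets the SAP modify the planned analyses and requires an amendment only for major changes to the primary endpoints, so the protocol text can be aligned at the next amendment.
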